5.2. General Methods

In general, number, percent, and 95% CI (Clopper-Pearson method) will be presented for binary endpoints. Descriptive summary statistics (n, Mean, Standard Deviation, Median, Min., Max.) will be presented for continuous endpoints. In addition, graphics may be used to present the data.

5.2.1. Analyses for Binary Data

Descriptive summary will be performed for binary endpoints for this study.

5.2.2. Analyses for Continuous Data

5.2.2.1. Longitudinal Continuous Data

Descriptive summary will be performed for longitudinal continuous endpoints for this study.

5.2.2.2. Non-longitudinal Continuous Data

Analysis of covariance (ANCOVA) will be used to analyze non-longitudinal continuous data, such as number of flare-free days over 52-week DB period. Age group (3 months- <12 years, ≥ 12 years), duration of the BID treatment in OL period (≤ 4 , >4 weeks), and ISGA score (clear [0], almost clear [1]) at randomization will be included in the model as covariates.

Least square (LS) estimates of mean values and the LS mean differences between crisaborole QD and vehicle QD groups will be derived from the model. The corresponding p-value, standard errors and 95% CI will also be derived from the model.

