5.1. Inclusion Criteria

Participants are eligible to be included in the study only if all of the following criteria apply:

Age

1. Participant must be 3 months of age or older at the time of signing the informed consent/assent (see [Appendix 8](#) for country-specific requirements).

Type of Participant and Disease Characteristics

2. Participant who meets the following AD criteria:
 - a. Confirmed clinical diagnosis of AD according to the criteria of Hanifin and Rajka (see [Appendix 6](#)).
 - b. AD treatment naïve, prior non-responder to emollient use, or has been previously treated with TCSs or TCIs.
 - c. AD involvement of $\geq 5\%$ Treatable % BSA (excluding the scalp) (see [Table 4](#)) at entry into the run-in period.

- d. ISGA score of Mild (2) or Moderate (3) at entry into the open-label run-in period.

Sex

3. Male or Female

Contraceptive use by men or women should be consistent with local regulations regarding the methods of contraception for those participating in clinical studies.

a. Male participants:

No contraception methods are required for male participants in this study.

b. Female participants:

- A female participant is eligible to participate if she is not pregnant or breastfeeding, and at least one of the following conditions applies:
 - Is not a woman of childbearing potential (WOCBP)

OR

- Is a WOCBP and using an acceptable contraceptive method as described in [Appendix 4](#) during the intervention period (at a minimum until after the last dose of study intervention). The investigator should evaluate the effectiveness of the contraceptive method in relationship to the first dose of study intervention.
- A WOCBP must have a negative highly sensitive ([Appendix 2](#)) pregnancy test (urine or serum as required by local regulations) within 7 days before the first dose of study intervention. If a urine test cannot be confirmed as negative (eg, an ambiguous result), a serum pregnancy test is required. In such cases, the participant must be excluded from participation if the serum pregnancy result is positive.
- Additional requirements for pregnancy testing during and after study intervention are located in [Appendix 2](#).
- The investigator is responsible for review of medical history, menstrual history, and recent sexual activity to decrease the risk for inclusion of a woman with an early undetected pregnancy

Informed Consent

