9.4.1.2. Analysis Methods

Endpoint	Statistical Analysis Methods
Primary	
Primary Analysis
 
Time of flare-free maintenance in the first QD period up until the onset of the first flare during the 52-week maintenance period will be analyzed using a log-rank test, stratified by age group, duration of the BID treatment in open-label period, and ISGA score (clear [0], almost clear [1]) at randomization to test the difference between crisaborole QD versus vehicle QD. The proportion of participants maintaining flare-free at each month until the first flare onset in the maintenance period will be estimated by the product limit method; the median time of flare-free up until the first flare onset will also be estimated by this method. This analysis will be based on Estimand 1 using the Evaluable-DB population (see Section 9.1 and Section 9.3 for estimands and populations).
 
Sensitivity/Supplementary Analysis
 
For the above primary analysis, the flare is based on the investigator assessment of ISGA; time of flare is ISGA assessment time. Before investigator assessment, the flare may already have occurred. As a sensitivity analysis, flare is defined as participants reported AD worsening event. Analysis method and intercurrent events handling are the same as above for the primary analysis.
 
Another sensitivity analysis is interval censoring survival analysis. Time of flare is between the time of participants reported AD worsening and the time of investigator confirmed ISGA ≥ 2. This analysis will be based on Estimand 1 using the Evaluable-DB population.

Secondary	
Number of flare-free days will be analyzed using an analysis of covariance model, with treatment, age, duration of the BID treatment in open-label period, and ISGA score (clear [0], almost clear [1]) at randomization as factors. The number of flare-free days is total duration across the double-blind QD periods in the study for each participant. This analysis will be based on Estimand 2 using the Evaluable-DB population.

Endpoint	Statistical Analysis Methods

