2.2. Study Design

Study C3291035 is a Phase 3, randomized, DB, vehicle-controlled study to assess the efficacy and safety of crisaborole ointment, 2%, QD as maintenance treatment and for the reduction of flare occurrence in participants (3 months of age and older) with mild-to-moderate AD.

Eligible participants will be enrolled to receive crisaborole BID in an OL period of up to a maximum of 8 weeks in duration. Responders to OL treatment at any time during this period will be randomized into the DB period in a 1:1 ratio to receive QD crisaborole or vehicle for 52 weeks.

[figure not shown]
During the OL period, a responder is defined as a participant who achieves both ISGA success (achieving a score of clear [0] or almost clear [1] with a ≥ 2 grade improvement from the OL baseline) and EASI50 (at least 50% improvement from the OL baseline in EASI).

Non-responders at the end of the 8-week OL period will be discontinued from the study. To yield a total of 162 first flare events in the DB period of the study, it is estimated that approximately 700 participants will be enrolled in the OL period for responder identification and that approximately 250 participants will be randomized into the DB period. Once adequate participants have been randomized, recruitment will stop; it is possible that less than 700 or up to 860 participants will be enrolled in the OL period.

CCI

Figure 1. Study Design Schematic

BID = twice daily; QD = once daily; ISGA = Investigator's Static Global Assessment; EASI = Eczema Area and Severity Index; EOT = End of treatment

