4. ANALYSIS SETS (POPULATIONS FOR ANALYSIS)

For purposes of analysis, the following populations are defined:

Population	Description
Enrolled	All participants who sign the informed consent form.
Evaluable-OL (Eval-OL)	All participants receiving at least 1 dose of study intervention in the OL period
Safety-OL (SAF-OL)	All participants receiving at least 1 dose of study intervention in the OL period. It is same as Evaluable-OL
Evaluable-DB (Eval-DB)	All randomized participants with success in ISGA and EASI50 criteria as responders at randomization and receiving at least 1 dose of study intervention in the DB period. Participants will be analyzed according to the intervention they are randomized to.
Safety-DB (SAF-DB)	All randomized participants receiving at least 1 dose of study intervention in the DB period. Participants will be analyzed according to the intervention they actually received.
Safety (SAF)	All participants receiving at least 1 dose of study intervention during the study.

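### The flare-free-days ANCOVA is valid but omits run-in severity, which ISGA at randomisation captures only in part; adding run-in EASI and ISGA may gain precision at almost no cost

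*SAP*

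**What the plan says.** SAP 5.2.2.2 specifies the ANCOVA for flare-free days, and SAP 6.2.1 refers back to it. The covariates are age group (cut at 12 years), "duration of the BID treatment in OL period" (cut at 4 weeks), and the item introduced as "ISGA score (clear [0], almost clear [1]) at randomization will be included in the model as covariates". SAP 3.5 names the same three for all the statistical models. Protocol 9.4.1.2 describes this model "with treatment, age, duration of the BID treatment in open-label period, and ISGA score (clear [0], almost clear [1]) at randomization as factors"; it says age where the SAP says age group.

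Three other rules determine what the ISGA factor can carry:

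- Entry (Protocol 5.1): "ISGA score of Mild (2) or Moderate (3) at entry into the open-label run-in period".
- Response (SAP 2.2; Protocol 4.1): ISGA 0 or 1 with at least a two-"grade improvement from the OL baseline) and EASI50".
- Analysis set (SAP 4, Evaluable-DB): "All randomized participants with success in ISGA and EASI50 criteria as responders at randomization", with at least one double-blind dose.

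SAP 3.5 lists ISGA, EASI, %BSA and pruritus at open-label baseline as baseline variables. None of these run-in values appears in the ANCOVA, in the stratified log-rank test (SAP 5.2.4) or among the subgroups (SAP 6.5). Protocol 6.3 names no stratification factor for the randomisation.

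**The concern.** An ANCOVA gains precision from baseline variables that predict the outcome. Severity before treatment is an obvious candidate for a relapse outcome, and the trial already holds it. The only severity term in the model is ISGA after a successful run-in, and the responder rule restricts that term to two values, one of which pools participants with different starting severity.

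This endpoint has a particular claim to attention. It is second in the fixed testing sequence (SAP 5.1.1), so failure there blocks any claim on number of flares and on the five pruritus subgroups. The documents state power only for the primary endpoint. Flare-free time is also truncated at censoring (SAP 6.2.1), so dropout adds to the variability of the outcome.

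**Working it through.** **1. The plan's own figure.** Protocol 9.2 gives about 96% power for the primary log-rank test with 162 events, hazard ratio 0.556 and two-sided 0.05. By Schoenfeld's formula, z = (√162 / 2) × |ln 0.556| − 1.960 = 6.364 × 0.587 − 1.960 = 1.776, which is 96.2% power. The figure reproduces, and this point does not affect it. There is no counterpart for flare-free days: no SD, effect size or power is given.

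**2. Which ISGA paths can occur in Evaluable-DB.**

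| Run-in ISGA | ISGA at randomisation | Gain | Responder? |
|---|---|---|---|
| 2 (mild) | 0 (clear) | 2 | yes |
| 2 (mild) | 1 (almost clear) | 1 | no |
| 3 (moderate) | 0 (clear) | 3 | yes |
| 3 (moderate) | 1 (almost clear) | 2 | yes |

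Apart from entry deviations, almost clear identifies moderate run-in disease exactly. Clear contains every mild participant and some moderates. Adding run-in ISGA can therefore only split the clear level.

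**3. How much of run-in ISGA the existing factor carries.** Let p be the share of randomised participants who were moderate at run-in, and q the share of those moderates who reached clear. The share of run-in ISGA variance explained by ISGA at randomisation is φ² = (1 − q)(1 − p) / (1 − p(1 − q)). For example, p = 0.6 and q = 0.3 give 0.7 × 0.4 / (1 − 0.42) = 0.48. The documents give neither p nor q, so these are assumptions:

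| p | q | φ² |
|---|---|---|
| 0.6 | 0.1 | 0.78 |
| 0.6 | 0.3 | 0.48 |
| 0.8 | 0.3 | 0.32 |
| 0.8 | 0.5 | 0.17 |
| 0.9 | 0.5 | 0.09 |

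For p from 0.5 to 0.95 and q from 0.1 to 0.7, φ² runs from 0.02 to 0.82. Run-in EASI and %BSA are carried only indirectly.

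**4. What extra covariates would buy.** If they explain a further share R² of the residual variance, the standard error is multiplied by √(1 − R²), and 250 participants act like 250 / (1 − R²). R² is assumed:

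| R² | SE falls by | 250 act like |
|---|---|---|
| 0% | 0% | 250 |
| 5% | 1 − √0.95 = 2.5% | 250 / 0.95 = 263 |
| 10% | 1 − √0.90 = 5.1% | 250 / 0.90 = 278 |

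**5. Where in that range.** An illustrative simulation of flare-free days used about 65% first flares (162/250 = 64.8%) and a treatment hazard ratio of 1/1.8. It assumed 15% dropout, residual frailty, and a moderate-versus-mild flare hazard ratio from 1 to 3. Adding run-in ISGA alone cut residual variance by 0% to 2.5%; adding run-in ISGA and EASI cut it by 0% to 6.3%. The upper end means an SE reduction of 1 − √0.937 = 3.2% and 250 / 0.937 = 267 effective participants. Power for this endpoint rose by 0 to about 3 points. Every severity input is an assumption.

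**6. The cost side.** The planned model uses five parameters (intercept, treatment, three factors), leaving about 245 residual degrees of freedom; two more covariates leave 243. If they explained nothing, the variance of the treatment difference would rise by roughly 245/243 − 1 = 0.8%, or about 0.4% in the SE.

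**The case against.** The strongest reply is that nothing is wrong with the plan. Under randomisation the ANCOVA estimates the treatment difference without bias and holds its type I error whether or not run-in severity is included. No passage says that severity before run-in still predicts flare-free days once everyone has met the ISGA and EASI50 criteria and the model already has ISGA at randomisation and run-in duration. The same three factors serve the log-rank, ANCOVA and Wilcoxon analyses, which is a coherent choice. Protocol 9.4.1.2 itself lists the factors, so the change reaches beyond the SAP.

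Most of this stands, and it limits the point to efficiency. It does not show a reason to leave the covariates out. Uniformity matters less here than for the other two tests: stratified rank methods need categories and suffer from sparse strata, whereas an ANCOVA takes a continuous covariate directly.

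A reader might also infer that ISGA at randomisation is a poor stand-in for run-in severity in general, or that the model gives no protection against chance imbalance in severity. The documents support neither. They never offer the factor as a proxy, it identifies moderate disease exactly at one of its two levels, and step 3 shows that it may carry little or most of run-in ISGA depending on case mix.

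**Conclusion.** The plan is valid, and this is a near-free improvement, not the correction of an error. What the documents establish is that run-in severity is collected, is not in the model, and is only partly represented by the ISGA factor. What they do not establish is that precision is actually lost, since that depends on a prognostic strength they do not report.

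On the assumed range of 0% to 10% further variance explained, the SE reduction is 0% to 5.1%. The simulated cases stop at 6.3%, so the lower part is more likely and zero is possible. A reader might infer a larger gain: 15% would give 1 − √0.85 = 7.8% and 250 / 0.85 = 294 participants. Nothing in the documents supports that figure, and it lies well beyond the simulated cases.

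A reader might also conclude that age should enter in years. That is optional and no part of this point: a straight line from 3 months to adulthood is a strong assumption of its own, and the 12-year cut matches a prespecified subgroup and the age boundary of several instruments.

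**What to change.** Before unblinding, amend SAP 5.2.2.2 and 6.2.1 so that the flare-free-days ANCOVA also includes open-label-baseline EASI as a continuous covariate and open-label-baseline ISGA as a two-level factor (mild, moderate). Keep the three existing factors. State that the expected gain is an assumption. Align Protocol 9.4.1.2 with the resulting list, and at the same time settle whether its age term means the SAP's two age groups.

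The cost is about two degrees of freedom and no new data. Protocol 9.4 requires major changes to key secondary analyses to appear in a protocol amendment as well, so the sponsor must decide whether added covariates count as major.

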5.2.3. Analyses for Categorical Data

The frequency and percentage for each category will be presented for category endpoints.

5.2.4. Analyses for Time-to-Event Data

Time-to-event analysis will be used to analyze time-to-event data.

Kaplan-Meier (product limit) method will be used for estimation of proportion of participants with event, time-to-event curve, median (95% CI) time-to-event.

A log-rank test, stratified by age group (3 months-<12 years, \geq 12 years), duration of the BID treatment in OL period (\leq 4, >4 weeks), and ISGA score (clear [0], almost clear [1]) at randomization, will be used to test the difference between crisaborole QD versus vehicle QD.

5.3. Methods to Manage Missing Data

For OL period, efficacy and PRO data summary will be based on Last Observation Carried Forward (LOCF) imputation data. For DB period, for descriptive statistics missing values will not be imputed. In addition, for safety endpoints, missing values will not be imputed.

For the continuous patient/observer reported outcomes variables, rules recommended by the developers of these instruments will be followed in the handling of missing data and in the scoring of the questionnaires when data are missing for one or more questionnaire items.

6. ANALYSES AND SUMMARIES

6.1. Primary Endpoint

The primary endpoint is flare-free maintenance until onset of first flare during the 52-week double-blind period.

6.1.1. Main Analysis

- Estimand strategy: Hypothetical ([Section 2.1.1](#)).
- Analysis Population: Evaluable-DB.
- Analysis method: Time-to-event analysis, Kaplan-Meier (product limit) method and log-rank test ([Section 5.2.4](#)).
- Intercurrent events: intercurrent events include discontinuation of treatment. If an intercurrent event (eg, death, dropout, loss to follow up, or end of study) occurs before the first flare, the duration of flare-free maintenance is the time from randomization to the first intercurrent event and is right censored. When a flare occurs first, the duration of flare-free maintenance is the time from randomization to the first flare and is not censored.

- Reporting results: At each month, the proportion of participants who had maintained flare-free status before the first flare, time-to-event curve, median (95% CI) time of maintaining flare-free, and number (%) of censored participants for each treatment group, and p-value from log-rank test will be presented.

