7.3. Lost to Follow up

A participant will be considered lost to follow-up if he or she repeatedly fails to return for scheduled visits and is unable to be contacted by the study site.

The following actions must be taken if a participant fails to return to the clinic for a required study visit:

- The site must attempt to contact the participant and reschedule the missed visit as soon as possible and counsel the participant on the importance of maintaining the assigned visit schedule and ascertain whether or not the participant wishes to and/or should continue in the study.
- Before a participant is deemed lost to follow up, the investigator/designee must make every effort to regain contact with the participant (where possible, 3 telephone calls and, if necessary, a certified letter to the participant's last known mailing address or local equivalent methods). These contact attempts should be documented in the participant's medical record.
- Should the participant continue to be unreachable, he/she will be considered to have withdrawn from the study.

Discontinuation of specific sites or of the study as a whole are handled as part of [Appendix 1](#).

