9.2. Sample Size Determination

A total of 162 events will provide approximately 96% power to detect a 1.8 ratio of median time of being flare-free (hazard ratio of 0.556) in the first QD period between crisaborole and vehicle at a significance level of 0.05 (2-sided, log-rank test). To get 162 events (first flare), approximately 250 participants who are eligible responders will be randomized (ratio=1:1) into the double-blind maintenance period of the study. When 162 events are observed, the randomization will be stopped even if less than 250 participants are randomized. On the other hand, if 250 participants are randomized, but 162 events cannot be reached, more participants will be randomized.

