10.9. Appendix 9: Alternative Study Procedures during COVID-19 Pandemic

In response to the COVID-19 pandemic, associated local or regional travel restrictions, and public health concerns, the following changes were incorporated into this protocol to clarify study procedures during the COVID-19 pandemic. These changes apply to the time period of the COVID-19 pandemic only when an in-clinic visit is not possible; after this time period normal study procedures should resume.

- In the event that the in-clinic study visits cannot be conducted, every effort should be made to follow-up on the safety of study participants by phone contact at the scheduled or unscheduled visits per the protocol Schedule of Activities. Video contact can be used if permitted by local regulations. During the phone (or video) contact, the following assessments should be performed:
 - a. Review and record study treatment including compliance and missed doses.
 - b. Review and record any AEs and SAEs since last contact, including but not limited to COVID-19 related events. The AE and SAE reporting process should be followed per protocol ([Section 8.3](#) and [Appendix 3](#)).
 - c. Review and record contraceptive method and results of urine pregnancy tests for female participants who are women of childbearing potential (See protocol [Appendix 4](#)).
 - d. Review and record any changes or new concomitant medications since last contact.
 - e. Record the review of the Bodymap with the participants, including information on any new lesions, and collect the Bodymaps in the participant's medical record when possible (See protocol [Section 8.1.4](#)).
 - f. Review eDiary for completion.

Note: For the participant to be randomized into the double-blind maintenance period of the study, the Randomization Day 1 visit must be an in-person visit with study site staff, which could be conducted as an in-home visit or an in-person visit at an alternative clinic, provided that these are permitted according to local regulations.

- If courier delivery of the study medication from study sites is allowable by law and local guidance, the study participants must provide verbal consent for providing the contact details for shipping purposes. The verbal consent should be documented in the source document. Tracking records of shipment including the chain of custody of the study medication must be kept in the participant's medical records.

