6.1.2. Sensitivity/Supplementary Analysis

For the above main analysis, the definition of flare is based on the investigator assessment of ISGA, time of flare is the assessment time when ISGA \geq 2. In addition, a sensitivity analysis will be performed where flare definition includes an AD worsening event (preferred term= Dermatitis atopic or Eczema) reported by a participant prior to a confirmatory ISGA \geq 2. In this analysis, the time of onset of such event will be used as the onset of the flare. If a participant reported an AD worsening event but the investigator assessment is not a flare at the subsequent visit, this event is not a flare. Estimand strategy, analysis population, analysis method and intercurrent events handling are the same as above for the main analysis.

Another sensitivity analysis is interval censoring survival analysis. Time of flare is between the time of participants reported AD worsening and the time of investigator confirmed ISGA \geq 2. Because the exact flare time is not known, the midpoint of the above interval will be used as the flare time. Estimand strategy, analysis population, analysis method and intercurrent events handling are the same as above for the main analysis.

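### Flare-free participants are censored at the dropout, loss-to-follow-up or end-of-study date rather than at their last ISGA, so time with no assessment can be credited as flare-free

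*SAP*

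**What the plan says.** **Censoring.** SAP 6.1.1 lists death, dropout, loss to follow-up and end of study as events that may precede a first flare. In those cases "the duration of flare-free maintenance is the time from randomization to the first intercurrent event and is right censored". Estimand 1 (SAP 2.1.1 and protocol 9.1.1) also censors at the event.

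**What counts as a flare.** SAP 6.1.2 states that in the main analysis "time of flare is the assessment time when ISGA" is 2 or more. Protocol section 8 requires a clinic visit to assess a flare suspected during a phone contact.

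**When ISGA is done.** In the schedule of activities, maintenance ISGA falls at in-clinic weeks 4, 8, 12, 16, 24, 32, 40, 48 and 52. Weeks 20, 28, 36 and 44 are phone contacts.

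**How follow-up ends.** Under protocol 7.3, loss to follow-up applies to a participant who "repeatedly fails to return for scheduled visits and is unable to be contacted by the study site". No date is assigned to it. The early discontinuation visit in protocol 7.2 is to be held where possible. Protocol 4.4 counts the Day 393 phone follow-up as part of completing the study.

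**Pandemic visits.** Appendix 9 says: "In the event that the in-clinic study visits cannot be conducted, every effort should be made to follow-up on the safety of study participants". Its list of remote assessments contains no ISGA.

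**Where the rule carries over.** SAP 6.2.1 truncates flare-free days at the same censoring point. Both sensitivity analyses in SAP 6.1.2 keep the main analysis's handling of intercurrent events.

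**The concern.** A time-to-event analysis should hold a participant at risk only while an event could be recorded. Here an event needs an in-person ISGA, but a participant who leaves is held at risk until the departure is dated. If that date falls after the last ISGA, the interval between them adds flare-free time that nobody assessed.

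Three reported results use that time: the monthly Kaplan-Meier flare-free proportions, the log-rank comparison, and total flare-free days, which is the first key secondary endpoint.

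The planned sensitivity analyses do not test this. One re-dates flares that ISGA later confirms. The other, called interval-censored, takes the midpoint between reported worsening and the confirming ISGA. Neither touches participants who had no further ISGA. SAP 5.3 gives no rule for missed ISGA visits in the time-to-event analysis.

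**Working it through.** **1. The plan's own figure.** Protocol 9.2 states: "A total of 162 events will provide approximately 96% power to detect a 1.8 ratio of median time". With a hazard ratio (HR) of 0.556, two-sided alpha 0.05 and 1:1 allocation, Schoenfeld's formula gives

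z = √(162 × 0.25) × |ln 0.556| − 1.96 = 6.364 × 0.587 − 1.96 = 1.776, so power = Φ(1.776) = 96.2%.

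The figure reproduces. It depends on the number of events, not on the censoring date, and is not in dispute.

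**2. Where the two rules differ.** Suppose a participant has an ISGA at week 16 and drops out at week 20.
- Dated at week 20, the participant is in the week-16 risk set and out of the week-24 risk set, exactly as under last-ISGA censoring. If flares are found only at scheduled visits, the log-rank result is identical.
- Dated 8 weeks late (20 + 8 = week 28), the participant is counted at risk at week 24 with no possibility of an event.

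**3. Why balance matters.** With constant hazards, the estimate is events divided by credited time. If a share s of an arm's credited time is unassessed, its hazard is multiplied by (1 − s). Hence

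HR(event date) ≈ HR(last ISGA) × (1 − s_crisaborole) / (1 − s_vehicle).

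Equal shares cancel. Unequal shares push the HR either way.

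**4. Simulated size.** From the documents: 250 participants, 1:1, HR 1/1.8, and the scheduled ISGA visits. The vehicle hazard was set so that 162 of 250 (64.8%) flare by week 52, giving 0.0270 per week: 1 − (e^−1.404 + e^−0.780)/2 = 1 − (0.246 + 0.458)/2 = 0.648. Assumed, because the documents give no rates: dropout over 52 weeks, dating lag, half of flares self-reported, and, in the last two rows, a 24-week remote-only window in 30% of participants. There were 500 runs per row. Each pair is the plan's rule v last-ISGA censoring.

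| Dropout vehicle/crisaborole, lag | Unassessed share | HR | Week-52 flare-free %, vehicle | Week-52 flare-free %, crisaborole | First-period flare-free-day difference |
|---|---|---|---|---|---|
| 20/20, none | 1.3% | 0.540 v 0.540 | 26.0 v 25.7 | 47.8 v 47.6 | 49.4 v 48.8 |
| 20/20, 8 wk | 4.5% | 0.542 v 0.540 | 27.3 v 25.7 | 49.0 v 47.6 | 50.8 v 48.8 |
| 15/30, 8 wk | 5.3% | 0.530 v 0.548 | 26.9 v 25.8 | 49.7 v 47.4 | 39.2 v 29.6 |
| 30/15, 8 wk | 4.9% | 0.556 v 0.533 | 28.0 v 25.6 | 48.7 v 47.6 | 60.8 v 65.8 |
| 15/30, 8 wk, remote | 8.7% | 0.534 v 0.553 | 29.0 v 26.0 | 51.4 v 47.3 | 36.8 v 24.4 |
| 30/15, 8 wk, remote | 8.3% | 0.560 v 0.533 | 30.1 v 25.6 | 50.5 v 47.7 | 59.3 v 61.5 |

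Read the differences within pairs, not the levels. In rows 3 and 4 the HR moves by −0.018 and +0.023, and the day difference by +9.6 and −5.1 (unrounded 60.76 − 65.84). With the remote window added, the day difference moves by +12.3 and −2.2. The day figures cover only the first flare-free period, whereas the endpoint sums all periods.

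As a check on step 3, the HR ratios in rows 3 and 4 are 0.530/0.548 = 0.97 and 0.556/0.533 = 1.04. Separate simulations under the null, with an 8-week lag and 30%/15% dropout, gave an HR of about 1.03 to 1.04, or 0.97 to 0.98 with the arms reversed. Type I error stayed near 5%.

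**The case against.** **The size comes from an assumed lag and imbalance, not from the rule alone.** This stands. Without lag the two rules agree to within 0.01 in HR. The documents give no dropout rate by arm, and protocol 7.2 expects withdrawal to be uncommon. Simulated power in row 4 is 91.4% v 95.2%, but at a fixed 250 participants, averaging about 144 events. The plan keeps randomizing until 162 events, so those powers are not the plan's.

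**Other contacts limit unassessed time.** Largely true. Participants are told to arrange a clinic visit for a suspected flare, phone contacts ask about flares, and discontinuation calls for a closing assessment where possible. Phone weeks are not blind time. None of this is guaranteed for someone who stops attending.

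**A reader might infer that pandemic remote visits are themselves censored as flare-free.** The documents do not say so: a remote visit is not an intercurrent event. Someone later seen in clinic is still assessed, and a persisting flare is counted, though late. Only a flare that clears in between is missed. Remote visits bear on this point only when no clinic ISGA follows.

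**Last-ISGA censoring is not free.** Also true. Flares self-reported between visits still count, while flare-free participants are cut back to their last visit. With 90% self-report, 30%/15% dropout and no lag, the null HR was 0.985 under the proposed rule and 0.993 under the plan's. With the arms reversed it was 1.009 v 1.001.

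**Conclusion.** The mismatch is real and no other section repairs it: events require an in-person ISGA, while censoring follows a departure date that for loss to follow-up is undefined. It merits a cheap improvement to the plan; it does not invalidate the primary test.

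With no dating lag or balanced unassessed time, the effect on the comparison is negligible. Under an assumed 8-week lag and 15% v 30% dropout, the HR shifts by about 0.02 to 0.04 and the first-period flare-free-day difference by about 5 to 10 days. Across the assumed settings, week-52 flare-free estimates rise by about 0 to 4.5 percentage points.

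A reader might infer that the rule favours crisaborole or inflates false positives. Neither is supported. The direction depends on which arm has more unassessed time, which the documents do not allow anyone to predict, and type I error stays near 5%.

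**What to change.** In SAP 2.1.1 and 6.1.1, mirrored in protocol 9.1.1:
- Censor participants with no recorded flare at their last in-person ISGA of 0 or 1 in the 52-week double-blind period, whether follow-up ended by dropout, loss or end of study. This also settles whether the Day 393 phone contact can extend flare-free time.
- Keep at risk anyone who misses ISGA visits or has remote visits but is later assessed in clinic, and count a flare found then.

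In SAP 6.2.1, truncate flare-free days at the same date. In SAP 6.1.2, run the interval-censored analysis with the interval from the last ISGA of 0 or 1 to the first ISGA of 2 or more. The event-date rule can be kept as a sensitivity analysis, with a stated date for loss to follow-up.

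The data are already collected. The cost is a few sentences, slightly shorter reported follow-up, and the very small upward push on hazards noted above. The change does not cure dropout caused by an unassessed flare: simulated at 30% vehicle and 10% crisaborole, such dropout gave an HR of 0.68 under both rules.
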